Serum Pregnancy Test protocol:		
Version or ID	Date (ddMMMyyyy)	Impact of the amendment on the statistical analysis
Final 2.1	19APR2021	Serum Pregnancy-specific

	Statistical Analysis Plan	
ARGX-113-2004	Final analysis	Final 1.0 of 7NOV2023

LIST OF ABBREVIATIONS

ADA	anti-drug antibody
ADaM	analysis data model
ADSL	subject-level analysis dataset
ADY	relative day
AE	adverse event
AESI	adverse event of special interest
ALQ	Above the upper limit of quantification
anti-D	anti-RhD
ASH	American Society of Hematology
ATC	anatomical therapeutic chemical
BLQ	Below the lower limit of quantification
BMI	Body Mass Index
bpm	beats per minute
CI	confidence interval
CKD-EPI	Chronic Kidney Disease Epidemiology Collaboration
C _{max}	Maximum observed serum concentration
CMH	Cochran-Mantel-Haenszel
CRF	case report form
CTCAE	common terminology criteria for adverse events
CTP	clinical trial protocol
C _{trough}	Serum concentration observed at pre-dose
CV%	coefficient of variation
DBP	diastolic blood pressure
ECG	electrocardiogram
eCRF	electronic case report form
eGFR	estimated glomerular filtration rate
EoS	end of study
FACIT	Functional Assessment of Chronic Illness Therapy
FACT-Th6	Functional Assessment of Cancer Therapy questionnaire-Th6
FAS	Full analysis set
HR	heart rate/hazard ratio
ICF	informed consent form

	Statistical Analysis Plan	
ARGX-113-2004	Final analysis	Final 1.0 of 7NOV2023

ICH	International Council for Harmonisation of Technical Requirements for Pharmaceuticals for Human Use
ID	identification
IgG	immunoglobulin G
IgGx	immunoglobulin G subtype
IMP	investigational medicinal product
█	█
█	█
IRR	injection-related reaction
IRT	interactive response technology
ISR	injection site reaction
ITP	immune thrombocytopenia
ITP-PAQ	ITP-Patient Assessment Questionnaire
IV	intravenous
IVD	in vitro diagnostic
IVIg	intravenous immunoglobulin
IWG	International Working Group
KM	Kaplan-Meier
LS	least square
M-CS	mental component summary
MedDRA	Medical Dictionary for Regulatory Activities
MMRM	mixed model for repeated measurements
NAb	neutralizing antibodies
NAP	not applicable
NCI	National Cancer Institute
OD	optical density
OR	odds ratio
P-CS	physical component summary
PD	Pharmacodynamic(s); PD analysis set
PK	Pharmacokinetic(s); PK analysis set
PP	per protocol
PRO	patient reported outcome
PT	preferred term
PYFU	patient years of follow-up

	Statistical Analysis Plan	
ARGX-113-2004	Final analysis	Final 1.0 of 7NOV2023

qw	weekly
q2w	every other week
QoL	quality of life

1. INTRODUCTION

This Statistical Analysis Plan (SAP) describes the final statistical analysis to be performed for the ARGX-113-2004 study.

This SAP covers the efficacy, safety, pharmacokinetic (PK), pharmacodynamics (PD), immunogenic and general characteristics parts of the statistical analysis. It specifies the analysis displays to be presented and describes the methods and procedures in a more elaborated way than in the statistical methods section of the clinical trial protocol (CTP).

The statistical analysis will process and present the results following the International Council for Harmonisation of Technical Requirements for Pharmaceuticals for Human Use (ICH) standards, in particular the ICH-E3¹, ICH-E6², and ICH-E9^{3,4} guidelines.

1.1 STUDY OBJECTIVES

According to the CTP, the primary objective of this study is:

- To evaluate the efficacy of efgartigimod PH20 SC compared to placebo PH20 SC in achieving a sustained platelet count response in patients with chronic primary immune thrombocytopenia (ITP), with a sustained platelet count response defined as platelet counts of at least $50 \times 10^9/L$ for at least 4 of the 6 visits between week 19 and 24 of the trial.

According to the CTP, the secondary objectives of this study are:

- To evaluate the efficacy of efgartigimod PH20 SC compared to placebo PH20 SC in overall platelet count response.
- To evaluate the incidence and severity of bleeding events while receiving treatment with efgartigimod PH20 SC compared to placebo PH20 SC.
- To evaluate the efficacy of efgartigimod PH20 SC compared to placebo PH20 SC in International Working Group (IWG) response
- To evaluate the safety and tolerability of efgartigimod PH20 SC administered weekly (qw) or every other week (q2w) compared to placebo PH20 SC.
- To evaluate the use of rescue treatment and changes in concurrent ITP therapy while receiving treatment with efgartigimod PH20 SC compared to placebo PH20 SC.
- To evaluate the effects of efgartigimod PH20 SC treatment on Quality of Life (QoL - Short Form-36 [SF-36]) measures and Patient Reported Outcomes (PRO) compared to placebo PH20 SC.
- To assess the immunogenicity of efgartigimod and rHuPH20.
- To assess the PK of efgartigimod PH20 SC.
- To assess the PD effects of efgartigimod PH20 SC.

	Statistical Analysis Plan	
ARGX-113-2004	Final analysis	Final 1.0 of 7NOV2023

According to the CTP, the exploratory objectives are:

- [REDACTED]
- [REDACTED]
- [REDACTED]
- [REDACTED]

1.2 STUDY ENDPOINTS

1.2.1 *Primary endpoint*

The primary endpoint is the proportion of patients with chronic ITP with a sustained platelet count response defined as achieving platelet counts of at least $50 \times 10^9/L$ for at least 4 of the 6 visits between week 19 and 24 of the study.

Participants who discontinue treatment prior to visit 24 due to lack of efficacy (e.g. more than 3 occurrences of rescue therapy) or due to an AE, and who have not achieved sustained platelet count response between week 19 and 24, are considered non-responders. Participants who receive rescue therapy at week 12 or later, or for whom dose and/or frequency of concurrent ITP therapies have increased at week 12 or later, are also considered non-responders.

1.2.2 *Secondary endpoints*

Key Secondary Efficacy Endpoints Subject to Alpha Control:

- Extent of disease control defined as the number of cumulative weeks over the planned 24-week treatment period with platelet counts of $\geq 50 \times 10^9/L$ in the chronic ITP population.
- Proportion of patients in the overall population (chronic and persistent ITP) with a sustained platelet count response defined as achieving platelet counts of at least $50 \times 10^9/L$ for at least 4 of the 6 visits between week 19 and 24 of the study.
- Proportion of patients in the overall population achieving platelet counts of at least $50 \times 10^9/L$ for at least 6 of the 8 visits between week 17 and 24 of the study.
- Incidence and severity of the WHO-classified bleeding events in the overall population.

Other Secondary Endpoints Not Subject to Alpha Control (overall population):

- Proportion of patients with overall platelet response defined as achieving a platelet count of $\geq 50 \times 10^9/L$ on at least 4 occasions at any time during the 24-week treatment period.
- Extent of disease control defined as the number of cumulative weeks until week 12, with platelet counts of $\geq 50 \times 10^9/L$.

	Statistical Analysis Plan	
ARGX-113-2004	Final analysis	Final 1.0 of 7NOV2023

- Proportion of patients with overall platelet response defined as achieving a platelet count of $\geq 50 \times 10^9/L$ on at least 4 occasions at any time until week 12.
- Mean change from baseline in platelet count at each visit.
- Time to response defined as the time to achieve 2 consecutive platelet counts of $\geq 50 \times 10^9/L$.
- The number of cumulative weeks over the planned 24-week treatment period with platelet counts $\geq 30 \times 10^9/L$ and at least $20 \times 10^9/L$ above baseline.
- In patients with baseline platelet count of $< 15 \times 10^9/L$, the number of cumulative weeks over the planned 24-week treatment period with platelet counts of $\geq 30 \times 10^9/L$ and at least $20 \times 10^9/L$ above baseline.
- Proportion of patients with an IWG response
- Proportion of patients with and IWG complete response
- Proportion of patients with an initial response
- Rate of receipt of rescue therapy (rescue per patient per month).
- Proportion of patients for whom dose and/or frequency of concurrent ITP therapies have increased at week 12 or later.
- Change from baseline in PRO (Functional Assessment of Chronic Illness Therapy [FACIT-Fatigue], Functional Assessment of Cancer Therapy questionnaire-Th6 [FACT-Th6]) and QoL (SF-36) at planned visits.
- Incidence and prevalence of antibodies to efgartigimod and rHuPH20.
- Titers of antibodies to efgartigimod and rHuPH20.
- Presence of neutralizing antibodies (NAb) against efgartigimod and rHuPH20, and titers of NAb against rHuPH20.
- Pharmacokinetic parameters of efgartigimod: serum efgartigimod concentration observed predose (C_{trough}).
- Pharmacodynamics markers: Total IgG and antiplatelet antibody levels.

Safety Evaluation:

- Incidence and severity of treatment-emergent adverse events (AEs), adverse events of special interest (AESIs), and serious adverse events (SAEs).
- Vital signs (VS), electrocardiogram (ECG), and laboratory assessments.

Exploratory Endpoints:

- [REDACTED]
- [REDACTED]
- [REDACTED]
- [REDACTED]

	Statistical Analysis Plan	
ARGX-113-2004	Final analysis	Final 1.0 of 7NOV2023

- [REDACTED]
- [REDACTED]

1.3 STUDY DESIGN

This is a phase 3, multicenter, randomized, double-blinded, placebo-controlled, parallel-group trial to evaluate the efficacy, safety, and effect on QoL/PRO of efgartigimod PH20 SC treatment in adult patients with primary ITP.

The total maximum trial duration per patient is up to 35 weeks:

- a screening period of up to 2 weeks
- a treatment period of 24 weeks
- an End-of-Treatment visit 1 week after visit 24
- a follow-up period of 8 weeks

The target population is adult patients with persistent or chronic primary ITP, having an average platelet count of $<30 \times 10^9/L$, and, at the start of the trial taking concurrent ITP treatment(s) and having received at least 1 prior therapy for ITP in the past, or not taking treatment for ITP but having received at least 2 prior treatments for ITP. If participants are receiving concurrent ITP therapies at baseline, these therapies should have been maintained at a stable dose and dosing frequency for 4 weeks before randomization.

As of week 12, the start or an increase in the dose and/or schedule of permitted concurrent ITP therapy is allowed for participants who have an “insufficient response” (ie, no platelet count of $\geq 30 \times 10^9/L$ in any of the visits during the last 4 weeks). These participants will be considered as “non-responders” for the primary endpoint analysis.

After confirmation of eligibility, the participants enter a 24-week treatment period and will be randomized to receive efgartigimod PH20 SC or placebo PH20 SC, qw from visits 1 to 4, and then from visits 5 to 16 either qw or q2w, adjusted according to their platelet counts. From visits 17 to 24, participants will be fixed on the dose schedule they were receiving at visit 16 or at the last visit at which IMP was administered before visit 16 (ie, either qw or q2w). Refer to CTP section 6.7 (dose regimen modification) and section 6.6.1 (permitted concomitant ITP therapies) for more details.

“Rescue therapy” is defined as an occurrence where the participant needs treatment with 1 or more rescue treatments. An “occurrence” is defined as a period of maximum 5 days where 1 or more rescue treatments are administered simultaneously or consecutively to the trial participant. The start date/time of the occurrence is the start of the administration of the first rescue treatment.

	Statistical Analysis Plan	
ARGX-113-2004	Final analysis	Final 1.0 of 7NOV2023

Rescue therapy is allowed postbaseline during the 24-week treatment period for participants with a platelet count of $<30 \times 10^9/L$ and 1 of the following:

- an immediate risk of bleeding or a clinically significant bleeding, or wet purpura
- requirement for urgent or emergent surgery (elective surgeries must be postponed until trial completion)

The following rescue therapies are permitted:

- IV methylprednisolone up to 1 g/day \times 1-3 days, or oral dexamethasone up to 40 mg/day \times 1-3 days, or oral prednisone up to 1 mg/kg/day \times 1-2 days
- Intravenous immunoglobulin (IVIg): up to 1 g/kg/day \times 1-2 days
- IV anti-D: up to 50-75 mcg/kg/day \times 1-2 days
- platelet transfusions

Participants completing the 24-week randomized trial period will perform the end-of-treatment visit and can enter the open-label extension trial (OLE - ARGX-113-2005). If a participant has had an SAE during the ARGX-113-2004 trial, his/her eligibility for the ARGX-113-2005 trial should be evaluated by the investigator and the sponsor's trial physician. The decision to enroll the participant will be made case by case. The platelet counts from the ARGX-113-2004 trial will be taken into account to assess the dosing frequency in ARGX-113-2005.

Participants who complete the 24-week trial period but who do not enter the open-label extension trial, or participants who discontinue the trial early, with the exception of participants who withdraw their consent, will be followed for 8 weeks for ongoing safety and efficacy monitoring.

For participants who discontinue the trial early, all the assessments listed for the Early Discontinuation visit as specified in the schedule of assessments (SoA, see appendix 9.5), will be performed.

End-of-Study is defined as last participant last visit in the ARGX-113-2004 trial.

1.4 EXPECTED SAMPLE SIZE

Approximately 180 participants with chronic ITP and up to 39 participants with persistent ITP were planned to be randomized in a 2:1 ratio to receive efgartigimod PH20 SC or placebo PH20 SC, respectively.

Non-Japanese participants were stratified according to the following factors:

- History of splenectomy (yes versus no)
- Receiving concurrent ITP therapies at baseline (yes versus no)

For Japanese patients enrolled in sites in Japan, there was no stratification, ie, randomization was performed within the full set of Japanese patients.

The null and alternative hypotheses are defined as $H_0: \pi_1 = \pi_2$ versus $H_A: \pi_1 \neq \pi_2$, where π_1 and π_2 are the population probabilities to achieve a sustained platelet count response (primary efficacy endpoint) for participants with chronic ITP receiving placebo PH20 SC and for participants with chronic ITP receiving efgartigimod PH20 SC, respectively.

	Statistical Analysis Plan	
ARGX-113-2004	Final analysis	Final 1.0 of 7NOV2023

In the placebo PH20 SC group, the response rate of participants with chronic ITP who reach the primary endpoint is expected to be $\leq 5\%$, while the response rate of participants with chronic ITP in the efgartigimod PH20 SC group is expected to be 21.8% (i.e. $\pi_1 = 0.05$ and $\pi_2 = 0.218$), based on the observed response rates in trial ARGX-113-1801. Given these assumptions, a total of $N = 180$ randomized participants with chronic ITP will ensure a power of at least 80% to reject the null hypothesis at a 1-sided significance level α of 0.025, based on Fisher's exact test.

For the first key secondary endpoint “extent of disease control” assuming distribution for cumulative number of weeks of disease control over the planned 24-week treatment period with platelet counts of $\geq 50 \times 10^9/L$ in the chronic ITP population similar to those observed in ARGX-113-1801, a total of $N=180$ participants will ensure a power of $>99\%$ (2-sided α of 0.05), conditionally on reaching the primary endpoint, to detect a significant difference between both treatment groups. For ensuring a power of at least 90%, a total number of $N=75$ participants would be needed, given these assumptions. Calculations are based on the Wilcoxon-Mann-Whitney test, where the O’Brien-Castelloe approach⁵ was taken to compute the power, taking into account a 2:1 allocation ratio to receive efgartigimod PH20 SC versus placebo PH20 SC.

1.5 RANDOMIZATION AND BLINDING

Approximately 180 participants with chronic ITP and up to 39 participants with persistent ITP will be randomized in a 2:1 ratio to receive efgartigimod PH20 SC or placebo PH20 SC, respectively. The results of all screening procedures have to be available prior to randomization (visit 1) to determine the eligibility for randomization into the study. Randomization should be performed as soon as possible after screening with a maximum of 2 weeks, however only after confirmation of eligibility of the patient. If a patient meets all the eligibility criteria and after approval from the sponsor, he/she will be randomized via interactive response technology (IRT). If a patient is not eligible, the patient should be recorded as a screen failure in the IRT system.

ARGX-113-2004 is a randomized, double-blinded, placebo-controlled study with limited access to the IMP treatment assigned.

1.6 INTERIM ANALYSIS

Not applicable.

1.7 SOFTWARE

SAS version 9.4 or higher will be used for programming.

1.8 VALIDATION MODEL

SGS Clinical Research (SGS CR) statistics (STAT) and pharmacokinetics (PK) standard operating procedures (SOPs) and work instructions (WIs) as effective at the time of the activity will be followed throughout the project, provided the applicable regulatory requirements are still met.

	Statistical Analysis Plan	
ARGX-113-2004	Final analysis	Final 1.0 of 7NOV2023

Analysis Data Model (ADaM) datasets (except subject-level analysis dataset [ADSL]), analysis tables, and listings will be validated according to model B: review by an independent person. The ADaM dataset ADSL, the primary endpoint, and following key secondary endpoints: extent of disease control and bleeding events will be validated according to model C: independent programming (see SOP.STAT.020 and SOP.PK.020).

	Statistical Analysis Plan	
ARGX-113-2004	Final analysis	Final 1.0 of 7NOV2023

2. GENERAL METHODOLOGY

2.1 ANALYSIS SETS

2.1.1 *Analysis sets*

The following analysis sets will be considered in the statistical analysis:

Table 1: Analysis sets

All screened participants set (SCR):	Participants who signed an informed consent to participate in this study
Full analysis set (FAS):	All randomized participants
FAS-chronic	Participants from the full analysis set including only participants with chronic ITP
Per-Protocol (PP):	Participants from the full analysis set, excluding the participants having any major protocol deviations
PP-chronic	Participants from the PP analysis set including only participants with chronic ITP
Safety analysis set (SAF):	All participants who received at least 1 dose or part of a dose
PK analysis set (PK):	Safety analysis set excluding placebo participants and including participants with at least one serum post dose PK measurement
PD analysis set (PD):	Safety analysis set including participants with at least one serum post dose PD measurement

Notes:

- Having signed an informed consent is defined as having a complete informed consent signature date in the database.
- Randomized is defined as having a complete randomization date in the database or any information to confirm randomization.

The efficacy analyses will be performed on the FAS or FAS-chronic where applicable. Sensitivity analyses of primary and key secondary efficacy endpoints will be performed on the PP or PP-chronic where applicable. General characteristics, safety and immunogenicity analyses (ADA, Antibodies, NAb) will be performed on the SAF. PK analysis will be performed on the PK. PD analysis will be performed on the PD.

2.1.2 *As planned versus as actual analysis*

For analyses performed on the SAF, PK and PD the actual treatment of the participant received will be considered. For analyses on the FAS, and PP, the planned treatment of the participant will be considered.

	Statistical Analysis Plan	
ARGX-113-2004	Final analysis	Final 1.0 of 7NOV2023

Only complete misallocation to a different treatment will lead to differences between planned and actual treatment in the analysis. Other occasional misdosings will not lead to a difference between planned treatment and actual treatment in the analysis.

2.2 PHASES AND TIME POINTS

2.2.1 *Phases and periods*

All events and assessments will be allocated to phases (see Table 2). The treatment phase consists of 24 weeks where all participants will receive injections of efgartigimod PH20 SC or placebo PH20 SC, including the End-of-Treatment visit, 1 week after visit 24. Only for participants who discontinue from the study or do not roll-over to ARGX-113-2005 a follow-up phase of 8 weeks is foreseen.

Table 2: Phase definition

Phase	Start	End ^a
Screening	Date of signing the informed consent form (ICF), with 00:00 added as time part.	First administration of the investigational medicinal product (IMP) date/time - 1 minute or End-of-Study date, with 23:59 added as time part (for participants not treated)
Treatment	First administration of the IMP date/time	End-of-Treatment visit end date, with 23:59 added as time part (for participants completing the treatment phase and not rolling over to 2005), or End-of-Study date, with 23:59 added as time part (for participants completing the treatment phase rolling over to 2005) or Early Discontinuation visit date ^b , with 23:59 added as time part (for participants early discontinuing from trial during the treatment phase).
Follow-up	Early Discontinuation visit date + 1 day, with 00:00 added as time part or End-of-Treatment visit date + 1 day, with 00:00 added as time part (for participants completing the treatment phase but not rolling over to study ARGX-113-2005).	End-of-Study date, with 23:59 added as time part

^a The last phase of a participant ends with the End-of-Study date, with 23:59 added as time part

^b If no Early Discontinuation visit was performed, use the End-of-Treatment date.

Table 3: Phase and period definition for the analysis of injection site reactions

Phase	Period	Start	End ^a
Treatment + Follow-up	Week 1-12	First efgartigimod administration date/time	First efgartigimod administration date + 83 days, with 23:59 added as time part
	Week 13-24	First efgartigimod administration date + 84 days, with 00:00 added as time part	First efgartigimod administration date + 167 days, with 23:59 added as time part

	Statistical Analysis Plan	
ARGX-113-2004	Final analysis	Final 1.0 of 7NOV2023

Week 24– 36	First efgartigimod administration date + 168 days, with 00:00 added as time part	First efgartigimod administration date + 251 days, with 23:59 added as time part
----------------	--	--

^a The last period ends on the date of End-of-Treatment visit date for participants completing the study and rolling over to study ARGX-113-2005, on the End-of-Study date with 23:59 added as time part for participants early discontinuing and for participants completing the study but not rolling over to study ARGX-113-2005

Adverse events (AEs) and concomitant medications will be allocated to phases as described in sections 5.1.2 and 3.5.2 respectively. All other assessments will be allocated to phases based on the assessment date/time.

In case of (partially) missing date(time) fields disabling allocation or date(time) equal to dosing date(time), information from visit label and protocol SoA will be used to allocate to the correct phase and period. If this is not possible, assessments will be handled as follows:

- Treatment phase versus screening phase: assessments will be allocated to the treatment phase unless the available parts of the assessments start or stop date(time) provide evidence for allocating to the screening phase.
- Follow-up phase versus treatment phase: assessments will be allocated to the treatment phase unless the available parts of the assessments start or stop date(time) provide evidence for allocating to the follow-up phase.

2.2.2 *Baseline and change from baseline*

The baseline value is defined as the last available non-missing value prior to first administration of the IMP. For total IgG, only results from the IVD assay will be considered, excluding screening samples.

Vital signs (VS) assessments on day 1 are considered pre-dose (no assessment time collected, pre-dose per protocol).

For parameters related to questionnaires, the baseline is the last value before or at the day of first administration of the IMP, independent of the time of administration.

Change from baseline at time point t = value at time point t – baseline value.

Percentage change from baseline at time point t is defined as follows:

- When baseline value is not zero: $100 * ((\text{value at time point } t - \text{baseline value}) / \text{baseline value})$
- When both baseline value and value at time point t are zero: 0
- When baseline value is zero and value at time point t is not zero: not calculated

2.2.3 *Relative day*

Relative days in the study (ADY) will be calculated according to the following rule:

- Concerned date < reference date: ADY = concerned date – reference date
- Concerned date ≥ reference date: ADY = concerned date – reference date + 1

	Statistical Analysis Plan	
ARGX-113-2004	Final analysis	Final 1.0 of 7NOV2023

Unless stated otherwise, the reference date is as follows:

- For assessments in screening and treatment phase: the date of first administration of study drug.
- For assessment in follow-up phase: the start date of the follow-up phase.

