2.4.3 Ordering in tables and listings

All tables will be presented per treatment, unless specified otherwise. In by-visit displays, worst-case will be shown last, if present.

In listings for general characteristics, results will be ordered by treatment and participant, unless specified otherwise.

All other listings will be ordered by treatment, participant, analysis visit, and time point, unless specified otherwise.

In tables showing several parameters, each parameter will begin on a new page and parameters will be sorted alphabetically, within the parameter category if applicable.

The efgartigimod PH20 SC treatment group will always be shown first, then the placebo PH20 SC treatment group.

	Statistical Analysis Plan	
ARGX-113-2004	Final analysis	Final 1.0 of 7NOV2023

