5.1.2 Derivation rules

Treatment-emergent adverse events (TEAE) are defined as AEs starting on or after first dose of IMP and up to and including 60 days after latest dose prior to the event. In case of a (partially) missing AE start date/time, the event will be considered as treatment-emergent, unless the available parts of the AE start date/time provide evidence not to do so.

Based on their start date/time, AEs will be allocated to the phase during which they started. Each AE will therefore be reported in only 1 phase. Phases are defined in section 2.2.1, Table 2. In case the AE start date/time is incomplete or missing and the AE could consequently be allocated to more than 1 phase, a worst-case allocation will be done: the AE will be allocated to the treatment phase unless the available parts of the AE start or stop date/time provide evidence for allocating to the screening phase/follow-up phase. AESIs will also be allocated to analysis periods (see section 2.2.1, Table 3). In case the AESI start date/time is incomplete or missing and the AESI could consequently be allocated to more than 1 period, it will be allocated to the first possible period.

Death is not considered an AE in itself but a ‘fatal’ outcome of an SAE.

An AE for which the study drug was discontinued is defined as an AE with action taken ‘drug withdrawn’.

Injection-related reactions (IRRs) will be defined as all AEs with a MedDRA preferred terms that are listed in either:

- MedDRA Hypersensitivity standardised MedDRA queries (SMQ) broad selection
- MedDRA Anaphylactic reaction SMQ broad selection
- MedDRA Extravasation events (injections, infusions and implants) SMQ broad selection, excluding implants

AND occurring within 48 hours of an injection, or within 2 days in case no AE start time is available. In case of partially missing AE start date, the AE will be considered as an IRR, unless the available parts of the AE start date provide evidence it did not occur within 48 hours of an injection.

	Statistical Analysis Plan	
ARGX-113-2004	Final analysis	Final 1.0 of 7NOV2023

Injection site reactions (ISR) will be defined as PTs in the MedDRA high level term of “injection site reactions”, regardless of the time of onset.

Two AESI types will be used: ‘Bleeding events’ as recorded on the AE section of the CRF and ‘Infections’ as defined using the MedDRA system organ class (SOC) ‘Infections and infestations’.

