5.1.3 Presentation of results

Tables will present TEAEs only. The AEs will be presented for the overall study duration, including AEs during the follow up. Pre-treatment AEs will only be listed.

An overview table will show the number and percentage of participants with at least 1 event and the number of events for the following:

- TEAEs
- Serious TEAEs
- Non serious TEAEs
- Grade ≥ 3 TEAEs
- Fatal TEAEs
- Treatment related TEAEs according to the principal investigator
- Procedures related TEAEs

	Statistical Analysis Plan	
ARGX-113-2004	Final analysis	Final 1.0 of 7NOV2023

- Serious treatment related TEAEs
- TEAEs for which the study was discontinued
- TEAEs for which the study drug was discontinued
- TEAEs for which the study drug was interrupted
- TEAEs of special interest: bleeding events
- TEAEs of special interest: infections
- ISR TEAEs
- IRR TEAEs
- TEAEs of hypersensitivity
- TEAEs of anaphylactic reaction

In addition, the number of events per participant years on study will be added to the overview table.

The overview table will be repeated, overall and by 12-week period (as defined in [Table 3](#)), specifically for ISR events, omitting the records related to TEAEs of special interest and ISR events.

Summary tables by MedDRA SOC and PT will show the number and percentage of participants with at least one event. The table of TEAEs will additionally show the number of events. The table of ISR events will be presented overall and by 12-week period (as defined in [Table 3](#)).

Summary tables by MedDRA SOC and PT will show the number and percentage of participants with at least 1 event. The table of TEAEs will additionally show the number of events.

Separate tables will be prepared for the following TEAEs:

- Serious TEAEs
- Non serious TEAEs
- Grade ≥ 3 TEAEs
- Fatal TEAEs
- Treatment related TEAEs according to the Principal Investigator
- TEAEs related to study procedures
- Serious treatment-related TEAEs
- TEAEs leading to discontinuation from the study
- TEAEs leading to discontinuation of study drug
- TEAEs for which the study drug was interrupted
- TEAEs of special interest: bleeding events
- TEAEs of special interest: infections
- ISR events
- Serious ISR events
- IRR events
- Serious IRR events
- TEAEs of hypersensitivity

	Statistical Analysis Plan	
ARGX-113-2004	Final analysis	Final 1.0 of 7NOV2023

- TEAEs of anaphylactic reaction

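### SAP Table 3 starts the 12-week injection-site-reaction periods at the first efgartigimod dose, a date placebo participants lack, so followed literally the placebo by-period columns hold no events

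*SAP*

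**What the plan says.** SAP 2.2.1 has two tables of time intervals. Table 2 defines the phases and starts the treatment phase, for everyone, at "First administration of the IMP date/time". Table 3 defines three periods for injection-site reactions. Its first period starts at "First efgartigimod administration date/time", and the three periods end at "First efgartigimod administration date + 83 days, with 23:59 added as time part", "First efgartigimod administration date + 167 days, with 23:59 added as time part" and "First efgartigimod administration date + 251 days, with 23:59 added as time part". The second and third periods start 84 and 168 days after the same date. All six cells therefore use the efgartigimod date, and none offers an alternative for placebo.

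The periods feed two displays. SAP 5.1.3 asks for the injection-site-reaction overview overall and by the Table 3 periods, and says of the summary by system organ class and preferred term: "The table of ISR events will be presented overall and by 12-week period". In the SAP 8.1 table list these are 14.3.1.15 and 14.3.1.16, both on the safety analysis set, and the second is marked top-line. The general layout rule in SAP 2.4.3 is "All tables will be presented per treatment, unless specified otherwise", so a placebo column is expected in each.

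**The concern.** A period dated from the first efgartigimod dose has no start and no end for someone who receives only placebo. The rule tells the programmer how to place each event, so the wording decides what the table shows.

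Placebo matters for this display. Protocol 6.1 gives both products the same 2000 U/mL of rHuPH20 by the same route, and Protocol 2.3.1 says local reactions are common when efgartigimod is given with PH20. The placebo column is what lets a reader separate the drug's local reactions from those of the vehicle and the injection, and the by-period layout shows whether that difference changes over time. With no placebo events in any period, that part of the table cannot be read. SAP 2.4.1 sets the denominator for event-type safety data at all participants in the analysis set per treatment and phase, so the cells could print as zeros rather than blanks, and zeros are easier to misread.

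**Working it through.** **Inputs**
- Period limits, in days after the anchor date: 0 to 83, 84 to 167, 168 to 251 (SAP Table 3).
- Anchor in Table 3: first efgartigimod dose. Anchor in Table 2 and for baseline (SAP 2.2.2): first IMP dose. Anchor for relative day in the screening and treatment phases (SAP 2.2.3): first study drug dose, where the SAP's definition of terms makes study drug either the active product or placebo.
- Placebo composition: the efgartigimod formulation with the active ingredient left out (Protocol 6.2.1).
- Planned size: about 180 chronic and up to 39 persistent participants, 2:1 (Protocol 9.3).

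**Step 1: the plan's own periods.** Length = end − start + 1.
- 83 − 0 + 1 = 84 days
- 167 − 84 + 1 = 84 days
- 251 − 168 + 1 = 84 days

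Each is 84/7 = 12 weeks, as intended. With the anchor date as day 1, they cover study days 1-84, 85-168 and 169-252, which are weeks 1-12, 13-24 and 25-36. The third is labelled Week 24-36, so its label overlaps Week 13-24 although its limits do not.

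**Step 2: place a reaction on each weekly dosing-visit day.** The 24 visits fall 0, 7, ..., 161 days after the first injection. Offsets 0 to 77 (12 visits) lie in the first period and 84 to 161 (12 visits) in the second.

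| Arm | Anchor as written | Anchor = first IMP dose |
|---|---|---|
| Efgartigimod | 12 + 12 = 24 of 24 | 12 + 12 = 24 of 24 |
| Placebo | 0 of 24 | 12 + 12 = 24 of 24 |

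Changing the anchor restores placebo and moves nothing for efgartigimod.

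**Step 3: is there another rule that supplies the date?**
- The fallback in SAP 2.2.1 (visit label and schedule) deals with missing or tied date fields of assessments. Adverse events are sent to SAP 5.1.2 instead.
- The period rule in SAP 5.1.2 reads "AESIs will also be allocated to analysis periods (see section 2.2.1, Table 3", and its fallback covers an incomplete start date of the event. It does not replace a missing anchor, and it names events of special interest, not injection-site reactions.
- Rolling over does not help. Under Protocol 6.8 the first extension dose comes on or after the end-of-treatment visit, and footnote a of SAP Table 3 closes the last period on that visit date for participants who roll over.
- Under SAP 2.1.2 a placebo participant given a stray efgartigimod dose is still analysed as placebo. That participant would have an anchor date, but a wrong one unless the stray dose was the first injection.

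**Step 4: who could be affected.** Placebo share at 2:1: 180/3 = 60 chronic and 39/3 = 13 persistent, so up to 73 of 219. This is a ceiling. Only those who have an injection-site reaction have an event to lose, and the documents give no rate for that.

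**The case against.** The strongest reply is that the intended meaning is plain. Table 3 assigns its periods to treatment plus follow-up, and Table 2 just above starts treatment at the first IMP dose for both arms. Footnote a ends the last period by completion and rollover status with no mention of arm. The protocol also uses the drug's name loosely for blinded product, for instance when it describes caregiver training (10.1.3) and dosing errors (8.5). A programmer would probably use the first IMP date, and both tables also carry overall columns, so a placebo arm with reactions overall and none in any period would stand out on review.

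Most of this stands: the text reads as a slip, and it would probably be caught. It does not make the rule correct. Elsewhere SAP 2.2 says IMP or study drug when it means both arms, so a programmer who used the IMP date would be departing from the final SAP. SAP 1.8 also gives these tables review by a second person; independent programming is kept for the subject-level dataset, the primary endpoint and two key secondary endpoints.

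A reader might go further and infer three things that the documents do not support.
- That the injection-site-reaction comparison loses its control arm. It does not: the overall columns of the same two tables, and the other adverse event tables, keep placebo.
- That efgartigimod's excess would be overstated by some number of points. The documents give no reaction rate for either arm, so any such figure would rest on assumed rates.
- That bleeding and infection results are damaged through the rule in SAP 5.1.2. The listed tables for these, 14.3.1.13 and 14.3.1.14, have no period breakdown.

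**Conclusion.** The point holds as a wording error in an operative rule, with a narrow effect. Read literally, Table 3 gives placebo participants no period, and the placebo by-period columns of Tables 14.3.1.15 and 14.3.1.16 would contain no events. This covers the whole placebo arm, up to 73 of 219 planned participants, apart from anyone given a stray efgartigimod dose.

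The displays are descriptive. No hypothesis test, type I error control, efficacy endpoint or overall safety count changes. The conclusion assumes that the table is programmed as written; if the first IMP date is used anyway, the output is right and only the document is wrong. The mislabelled third period is a separate, smaller slip in the same table.

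**What to change.** In all six start and end cells of SAP Table 3, date the boundary from the first administration of the IMP, as Table 2 does, and keep the day offsets. Relabel the third period, +168 to +251 days, as Week 25-36.

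The cost is a wording change in one SAP table. It needs no new data, does not affect participants, and leaves the allocation of efgartigimod events as it is.
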